6.3 Dose Modifications for Pembrolizumab (MK-3475)

Both serious and non-serious adverse events associated with pembrolizumab may represent an immunologic etiology and may occur shortly after the first dose or several months after the last dose. Pembrolizumab must be withheld for drug-related toxicities and severe or life-threatening AEs.

Dose interruptions are permitted in the case of medical/surgical events or logistical reasons not related to study therapy (e.g., elective surgery, unrelated medical events, patient vacation and/or holidays). Patients should be placed back on study therapy within 3 weeks of the scheduled interruption. The reason for interruption should be documented in the patient's study record.

Patients should receive appropriate supportive care measures as deemed necessary by the treating investigator. Suggested supportive care measures for the management of adverse events with potential immunologic etiology guidelines include the use of oral or IV treatment with corticosteroids as well as additional anti-inflammatory agents if symptoms do not improve with administration of corticosteroids. Note that several courses of steroid tapering may be necessary as symptoms may worsen when the steroid dose is decreased. For each disorder, attempts should be made to rule out other causes such as metastatic disease or bacterial or viral infection, which might require additional supportive care. The treatment guidelines are intended to be applied when the investigator determines the events to be related to pembrolizumab.

Note: If after the evaluation the event is determined not to be related, the investigator does not need to follow the treatment guidance as outlined below.

It may be necessary to perform conditional procedures such as bronchoscopy, endoscopy, or skin photography as part of the evaluation of the event.

General instructions:

1. Severe and life-threatening irAEs should be treated with IV corticosteroids followed by oral steroids. Other immunosuppressive treatment should begin if the irAEs are not controlled by corticosteroids.

2. Pembrolizumab must be permanently discontinued if the irAE does not resolve or the corticosteroid dose is not ≤ 10 mg/day within 12 weeks of the last pembrolizumab treatment.
3. The corticosteroid taper should begin when the irAE is \leq Grade 1 and continue at least 4 weeks.
4. If pembrolizumab has been withheld, pembrolizumab may resume after the irAE decreased to \leq Grade 1 after corticosteroid taper.

irAEs	Toxicity grade (CTCAE V5.0)	Action with pembrolizumab	Corticosteroid and/or other therapies	Monitoring and follow-up
Pneumonitis	Grade 2	Withhold	
 • Administer corticosteroids (initial dose of 1 - 2 mg/kg prednisone or equivalent) followed by taper • Add prophylactic antibiotics for opportunistic infections 	
 • Monitor participants for signs and symptoms of pneumonitis • Evaluate participants with suspected pneumonitis with radiographic imaging and initiate corticosteroid treatment
	Recurrent Grade 2, Grade 3 or 4	Permanently discontinue		
Diarrhea / Colitis	Grade 2 or 3	Withhold	
 • Administer corticosteroids (initial dose of 1 - 2 mg/kg prednisone or equivalent) followed by taper 	
 • Monitor participants for signs and symptoms of enterocolitis (ie, diarrhea, abdominal pain, blood or mucus in stool with or without fever) and of bowel perforation (ie, peritoneal signs and ileus) • Participants with \geqGrade 2 diarrhea suspecting colitis should consider GI consultation and performing endoscopy to rule out colitis • Participants with diarrhea/colitis should be advised to drink liberal quantities of clear fluids. If sufficient oral fluid intake is not feasible, fluid and electrolytes should be substituted via IV infusion
	Recurrent Grade 3 or Grade 4	Permanently discontinue		
AST or ALT elevation or Increased Bilirubin	Grade 2 ^a	Withhold	
 • Administer corticosteroids (initial dose of 0.5 - 1 mg/kg prednisone or equivalent) followed by taper 	
 • Monitor with liver function tests (consider weekly or more frequently until liver enzyme value returned to baseline or is stable)
	Grade 3 ^b or 4 ^c	Permanently discontinue	
 • Administer corticosteroids (initial dose of 1 - 2 mg/kg prednisone or 	

			equivalent) followed by taper	
Type 1 diabetes mellitus (T1DM) or Hyperglycemia	New onset T1DM or Grade 3 or 4 hyperglycemia associated with evidence of β -cell failure	Withhold ^d	
 Initiate insulin replacement therapy for participants with T1DM Administer anti-hyperglycemic in participants with hyperglycemia 	
 Monitor participants for hyperglycemia or other signs and symptoms of diabetes
Hypophysitis	Grade 2	Withhold	
 Administer corticosteroids and initiate hormonal replacements as clinically indicated 	
 Monitor for signs and symptoms of hypophysitis (including hypopituitarism and adrenal insufficiency)
	Grade 3 or 4	Withhold or permanently discontinue ^d		
Hyperthyroidism	Grade 2	Continue	
 Treat with non-selective beta-blockers (eg, propranolol) or thionamides as appropriate 	
 Monitor for signs and symptoms of thyroid disorders
	Grade 3 or 4	Withhold or permanently discontinue ^d		
Hypothyroidism	Grade 2, 3, 4	Continue	
 Initiate thyroid replacement hormones (eg, levothyroxine or liothyronine) per standard of care 	
 Monitor for signs and symptoms of thyroid disorders
Nephritis: grading according to increased creatinine or acute kidney injury	Grade 2	Withhold	
 Administer corticosteroids (prednisone 1 – 2 mg/kg or equivalent) followed by taper 	
 Monitor changes of renal function
	Grade 3 or 4	Permanently discontinue		
Myocarditis	Grade 1 or 2	Withhold	
 Based on severity of AE administer corticosteroids 	
 Ensure adequate evaluation to confirm etiology and/or exclude other causes
	Grade 3 or 4	Permanently discontinue		
All Other immune-related AEs	Persistent Grade 2	Withhold	
 Based on severity of AE administer corticosteroids 	
 Ensure adequate evaluation to confirm etiology or exclude other causes
	Grade 3	Withhold or discontinue based on the event ^e		
	Recurrent Grade 3 or Grade 4	Permanently discontinue		

^a AST/ALT: >3.0 - 5.0 x ULN if baseline normal; >3.0 - 5.0 x baseline, if baseline abnormal; bilirubin:>1.5 - 3.0 x ULN if baseline normal; >1.5 - 3.0 x baseline if baseline abnormal

^b AST/ALT: >5.0 to 20.0 x ULN, if baseline normal; >5.0 - 20.0 x baseline, if baseline abnormal; bilirubin:>3.0 - 10.0 x ULN if baseline normal; >3.0 - 10.0 x baseline if baseline abnormal

^c AST/ALT: >20.0 x ULN, if baseline normal; >20.0 x baseline, if baseline abnormal; bilirubin: >10.0 x ULN if baseline normal; >10.0 x baseline if baseline abnormal

^d The decision to withhold or permanently discontinue pembrolizumab is at the discretion of the investigator or treating physician. If control achieved or \leq Grade 2, pembrolizumab may be resumed.

^e Events that require discontinuation include but are not limited to: Guillain-Barre Syndrome, encephalitis, Stevens-Johnson Syndrome and toxic epidermal necrolysis.

Note: PRO-CTCAE data should not be used for determining dose delays or dose modifications

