5.6 Duration of Follow Up

Patients will be followed for 12 months after removal from study treatment or until death, whichever occurs first. Patients will be followed every three months by a telephone call or letter to assess vital status. Patients removed from study for unacceptable adverse event(s) will be followed longer if needed until resolution or stabilization of the adverse event.

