NOTE: Protocol specific exceptions to expedited reporting of serious adverse events are found in the Specific Protocol Exceptions to Expedited Reporting (SPEER) portion of the CAEPR.

Expedited AE reporting timelines are defined as:

- “24-Hour; 5 Calendar Days” - The AE must initially be submitted electronically within 24 hours of learning of the AE, followed by a complete expedited report within 5 calendar days of the initial 24-hour report.
- “10 Calendar Days” - A complete expedited report on the AE must be submitted electronically within 10 calendar days of learning of the AE.

¹Serious adverse events that occur more than 30 days after the last administration of investigational agent/intervention and have an attribution of possible, probable, or definite require reporting as follows:

Expedited 24-hour notification followed by complete report within 5 calendar days for:

- All Grade 3, 4, and Grade 5 AEs

Expedited 10 calendar day reports for:

- Grade 2 AEs resulting in hospitalization or prolongation of hospitalization

²For studies using PET or SPECT IND agents, the AE reporting period is limited to 10 radioactive half-lives, rounded UP to the nearest whole day, after the agent/intervention was last administered. Footnote “1” above applies after this reporting period.

Effective Date: May 5, 2011

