7.4 Routine Adverse Event Reporting

All Adverse Events **must** be reported in routine study data submissions. **AEs reported expeditiously through CTEP-AERS must also be reported in routine study data submissions.**

Adverse event data collection and reporting, which are required as part of every clinical trial, are done to ensure the safety of patients enrolled in the studies as well as those who will enroll in future studies using similar agents. AEs are reported in a routine manner at scheduled times during the trial using Medidata Rave. For this trial the Adverse Event CRF is used for routine AE reporting in Rave.

Symptomatic Adverse Events reported by patients through PRO-CTCAE are not safety reporting and may be presented with other routine AE data.

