- g: For Phase 2, submission of a tissue sample at pre-registration is required to perform the mesothelin expression assay to establish eligibility. Archived tumor tissue may be submitted; if archived tumor tissue is not available to establish eligibility, a fresh tumor tissue sample must be obtained by biopsy. If a biopsy is required, it may be performed ≤ 28 days prior to start of therapy. For Phase 1 subjects, submission of archived tumor tissue, if available, is required for mesothelin expression testing. Please refer to Section 9.
- h: For subjects in both Phases 1 and 2, submission of a stored tissue sample is mandatory, *if available*, for the tissue expression of PD-L1: do **not** perform a biopsy solely to provide tissue for this correlative. Tumor tissue may be submitted as blocks or slides; please refer to section 9.

i: Blood samples for correlates are collected as follows (see also Section 9):

- 1) Phase 1 and Phase 2 Group 2 patients only: Pharmacokinetics of anetumab raptansine (including anetumab raptansine ADC, anetumab raptansine total antibody, and DM4/DM4-Me) on C1D1: pre-treatment, end of anetumab raptansine infusion (+/- 15 minutes), and 7 hours after the end of anetumab raptansine infusion (+/- 15 minutes); C1D8: any time. Note: These may be discontinued for patients who discontinue anetumab raptansine.
- 2) Phase 1 and Phase 2 Group 2 patients only: Anti-anetumab raptansine antibodies (including anetumab raptansine ADA and neutralizing antibodies) pre-dose on Day 1 of Cycles 1, 3, 6 and 9 and pre-dose every 3 months after cycle 9 in the first year and every 6 months in the second year of treatment. Note: These may be discontinued for patients who discontinue anetumab raptansine.
- 3) Megakaryocyte Potentiating Factor: pre-study, C2D1, and C4D1.
- 4) Mononuclear Phagocyte System-Fc γ R: C1D1, C1D8, C3D1 and C3D8.
- 5) Chemokine Mediators of Mononuclear Phagocyte System: C1D1, C1D8, C3D1 and C3D8.
- 6) Bim in Tumor Reactive T cells and soluble PD-L1: pre-study, C2D1, and C4D1.

j: For sites and patients that agree to participate, PRO-CTCAE is completed by ePRO application on patients' personal devices or on a tablet kept at the study site weekly during the first 3 cycles and at off-study. Questionnaires should be administered prior to treatment on days study treatment is administered. See Appendices C and D.

k: Off-study evaluation to be performed at 30 ± 3 days after the last dose of study drug.

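### Scheduled adverse-event evaluation stops about 30 days after the last dose, although the protocol expects pembrolizumab events months later, and the existing three-monthly contacts do not ask about them

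*Combined protocol and SAP*

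**What the plan says.** Section 6.3 states that pembrolizumab events, both serious and non-serious, "may represent an immunologic etiology and may occur shortly after the first dose or several months after the last dose". Both phase 2 groups receive pembrolizumab on the same regimen (5.1).

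In the study calendar (section 10), the adverse-event row runs from cycle 1 to the off-study column. Footnote k fixes that column: "Off-study evaluation to be performed at 30 ± 3 days after the last dose of study drug".

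For the time after treatment, section 5.6 says: "Patients will be followed for 12 months after removal from study treatment or until death, whichever occurs first". The content of the contacts is given as: "Patients will be followed every three months by a telephone call or letter to assess vital status". Section 5.7 repeats both statements. One group is followed more closely: "Patients removed from study for unacceptable adverse event(s) will be followed longer if needed until resolution or stabilization of the adverse event".

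Reporting does not stop at day 30. Footnote 1 to the table in 7.3.3 deals with serious events that start later than that and are at least possibly related. It requires a 24-hour notification for "All Grade 3, 4, and Grade 5 AEs" and a 10-day report for "Grade 2 AEs resulting in hospitalization or prolongation of hospitalization". It sets no end date. Section 7.4 adds that "AEs reported expeditiously through CTEP-AERS must also be reported in routine study data submissions".

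Section 13.5.4 compares related grade 3 or higher event rates between the arms and names no time window. The stopping rule in 13.7.3 has no post-dose cut-off either.

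**The concern.** The protocol names a risk period of several months after the last dose for a drug given in both arms, and it says that the period covers non-serious events as well. Its schedule for asking about adverse events covers only about the first month of that period. The patients are still being contacted after that, but not about toxicity.

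Two things are at stake. The first is the completeness of the safety profile: a late immune event that does not come to the site's notice will not be in the data. The second is the meaning of the rates in 13.5.4. With no window stated, the comparison would pool events found at scheduled evaluations with whatever later serious events happened to reach the site. A reader could not tell what period the rate describes.

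**Working it through.** There is no figure in the plan to reproduce here. The check sets the sections side by side and measures how much of the follow-up has no planned enquiry.

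**1. Who has to report, and who asks, after the 30-day visit**

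| Late event | Duty to report | Planned contact that asks |
|---|---|---|
| Related, serious, grade 3 to 5 | Yes (7.3.3 footnote 1, then 7.4) | None, except that a death is found by the vital-status contact |
| Related, serious, grade 2 with hospitalization | Yes (same) | None |
| Related, non-serious | No specific rule after day 30; only the general statements in 7.3.1 and 7.4 that all events are collected | None |
| Event that led to removal | Followed until resolved or stable (5.6) | Yes, for that event |

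The general statements in 7.3.1 and 7.4 name no cut-off. However, 7.3.1 ties the form to treatment or reporting periods and to the investigator learning of the event, and 7.4 speaks of scheduled times. The calendar has no scheduled adverse-event time after the off-study visit. Medication records do not fill the gap: after day 30, section 5.4 asks for them only in connection with serious events.

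**2. Share of follow-up without a scheduled evaluation**

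Inputs: visit at 30 ± 3 days (section 10, footnote k); follow-up of 12 months (5.6). Assumption: the 12 months start at the last dose.

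- Visit at day 30: 1 − 30/365.25 = 0.918
- Visit at day 27: 1 − 27/365.25 = 0.926
- Visit at day 33: 1 − 33/365.25 = 0.910

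So about 92% (91% to 93%) of the follow-up, or 12 × 0.918 = 11.0 months, has no planned adverse-event enquiry. This is a share of time, not of events.

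**3. Contacts already planned**

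12 months / 3 months = 4 contacts per patient. For the 98 evaluable phase 2 patients, that is at most 98 × 4 = 392 contacts; for the maximum phase 2 accrual of 110, it is 110 × 4 = 440.

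**4. What cannot be calculated**

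The number of events missed equals the late-event rate, times the share that the site does not hear of, times the number of patients. The documents give neither of the first two quantities, so no count is offered.

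**The case against.** The strongest reply is that the plan already has a sensible two-tier scheme: active collection to 30 days, then mandatory reporting of related serious events. Section 6.3 is guidance on managing toxicity and does not define a data-collection window. The events that matter most are covered. Deaths and life-threatening events are serious by the definition in 7.3.3, so late related ones are reportable, enter the routine data and count under 13.7.3, which applies at any time. Both arms have the same pembrolizumab regimen and follow-up rules. The primary endpoint is response and is not touched. Moreover, section 5.4 prohibits no therapy during post-treatment follow-up, so late events may arise under other treatment and be hard to attribute.

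Much of this stands, and it rules out several stronger readings that a reader might infer:

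- That adverse-event collection ends at day 30. It does not; footnote 1 of 7.3.3 and section 7.4 keep related serious events in the data with no end date.
- That late non-serious events are barred from the database. No text says so; what is missing is a scheduled occasion to ask.
- That the stopping rule cannot see late events. It can count any that the site learns of.
- That the between-arm comparison is biased. This would need the timing of, or reasons for, stopping treatment to differ by arm in a way that changes what is heard. The documents do not show that, and no direction can be given.

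What the reply does not answer is that a duty to report is not a means of finding events. Even if the list in footnote 1 is read broadly, as covering every related event of grade 3 or higher, the duty starts only when someone tells the site. Patients who stop for progression, at the 24-month limit or by choice have no planned contact that asks. The attribution problem is real, but it bears on how the late data are analysed; it is not a reason to leave them uncollected.

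**Conclusion.** The point holds as a gap in active ascertainment. After the off-study visit, late non-serious immune events have no scheduled collection, and late serious ones depend on the site learning of them. Late immune toxicity may therefore be under-ascertained in both arms.

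The size that can be stated is the unsolicited time found above. It rests on the assumption that follow-up starts at the last dose, and on reading the contacts in 5.6 and 5.7 as limited to the purpose they state. It would be tempting to turn this into an expected number of missed events, or to say that under-reporting is established. The documents supply no rates for either step.

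The effect on the planned analyses is limited. Response, and the phase 2 decision based on it, are unaffected. For 13.5.4, the main defect is that the time window is not defined. The change is worth making because it improves safety data at contacts that will take place anyway.

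**What to change.** - **Sections 5.6 and 5.7:** have the existing three-monthly contacts ask, besides vital status, about any new or worsening event at least possibly related to study treatment (immune-related events in particular), and whether new anti-cancer therapy has started, with its date.
- **Section 10:** extend the adverse-event row, with a footnote, to these contacts.
- **Section 13.5.4:** make the between-arm grade 3 or higher comparison on events with onset up to the 30-day visit, where ascertainment is scheduled in both arms. Tabulate later related events separately by arm, flagged by whether they began before or after the start of subsequent therapy.

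The cost is two scripted questions at contacts already planned, one calendar line and one extra table. No new visit, procedure or staff is needed. The downsides are that reports by telephone or letter are less complete than clinic assessments, attribution is harder once other therapy has begun, and reported late-event counts will rise slightly. The separate late table keeps these weaknesses out of the main comparison. Nothing here changes dosing, treatment or clinical management.

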6.4 Continuation of Therapy When One Agent is Held or Discontinued

Patients who participate in the Phase 1 portion of this trial or are assigned to Treatment Group 2 (the combination of anetumab ravidansine and pembrolizumab) may continue to receive one agent if the other is held or discontinued for toxicity, and the toxicity is clearly attributable to the held or discontinued agent. If the toxicity in question is possibly related to either agent, then both agents should be held. These decisions may be discussed with the Principal Investigator.

7. ADVERSE EVENTS: LIST AND REPORTING REQUIREMENTS

Adverse event (AE) monitoring and reporting is a routine part of every clinical trial. The following list of AEs (Section 7.1) and the characteristics of an observed AE (Sections 7.2 and 7.3) will determine whether the event requires expedited reporting via the CTEP Adverse Event Reporting System (CTEP-AERS) in addition to routine reporting.

Clinician graded CTCAE is the AE (adverse event) safety standard. PRO-CTCAE items are to complement CTCAE reporting. Patients will respond to PRO-CTCAE items but no protocol directed action will be taken. The specific PRO-CTCAE items for this protocol can be found in Appendices C and D.

7.1 Comprehensive Adverse Events and Potential Risks List (CAEPRs)

7.1.1 Comprehensive Adverse Events and Potential Risks list (CAEPR) for **Anetumab ravidansine (BAY 94-9343, NSC 791065)**

The Comprehensive Adverse Events and Potential Risks list (CAEPR) provides a single list of reported and/or potential adverse events (AE) associated with an agent using a uniform presentation of events by body system. In addition to the comprehensive list, a subset, the Specific Protocol Exceptions to Expedited Reporting (SPEER), appears in a separate column and is identified with bold and italicized text. This subset of AEs (SPEER) is a list of events that are protocol specific exceptions to expedited

reporting to NCI (except as noted below). Refer to the 'CTEP, NCI Guidelines: Adverse Event Reporting Requirements' http://ctep.cancer.gov/protocolDevelopment/electronic_applications/docs/aeguidelines.pdf for further clarification. Frequency is provided based on 652 patients. Below is the CAEPR for Anetumab ravtansine (BAY 94-9343).

NOTE: Report AEs on the SPEER **ONLY IF** they exceed the grade noted in parentheses next to the AE in the SPEER. If this CAEPR is part of a combination protocol using multiple investigational agents and has an AE listed on different SPEERs, use the lower of the grades to determine if expedited reporting is required.

Version 2.4, November 14, 2019¹

Adverse Events with Possible Relationship to Anetumab ravtansine (BAY 94-9343) (CTCAE 5.0 Term) [n= 652]			Specific Protocol Exceptions to Expedited Reporting (SPEER)
Likely (>20%)	Less Likely (<=20%)	Rare but Serious (<3%)	
BLOOD AND LYMPHATIC SYSTEM DISORDERS			
	Anemia		
EYE DISORDERS			
	Blurred vision		Blurred vision (Gr 2)
	Dry eye		Dry eye (Gr 2)
Eye disorders - Other (corneal disorder) ²			Eye disorders - Other (corneal disorder)² (Gr 2)
	Keratitis		
GASTROINTESTINAL DISORDERS			
	Abdominal pain		
	Constipation		
Diarrhea			Diarrhea (Gr 2)
	Gastroesophageal reflux disease		
Nausea			Nausea (Gr 2)
	Vomiting		Vomiting (Gr 2)
GENERAL DISORDERS AND ADMINISTRATION SITE CONDITIONS			
Fatigue			Fatigue (Gr 2)
	Fever		
INJURY, POISONING AND PROCEDURAL COMPLICATIONS			
	Infusion related reaction		
INVESTIGATIONS			
	Alanine aminotransferase increased		Alanine aminotransferase increased (Gr 2)
	Alkaline phosphatase increased		
	Aspartate aminotransferase increased		Aspartate aminotransferase increased (Gr 2)
	Blood bilirubin increased		
	Lipase increased		
	Lymphocyte count decreased		
		Neutrophil count decreased	
	Platelet count decreased		Platelet count decreased (Gr 2)
	Weight loss		
	White blood cell decreased		
METABOLISM AND NUTRITION DISORDERS			
Anorexia			Anorexia (Gr 2)
MUSCULOSKELETAL AND CONNECTIVE TISSUE DISORDERS			
	Arthralgia		
	Muscle cramp		
	Myalgia		

Adverse Events with Possible Relationship to Anetumab raptansine (BAY 94-9343) (CTCAE 5.0 Term) [n= 652]			Specific Protocol Exceptions to Expedited Reporting (SPEER)
Likely (>20%)	Less Likely (<=20%)	Rare but Serious (<3%)	
NERVOUS SYSTEM DISORDERS			
	Dysgeusia		
	Nervous system disorders - Other (neuropathy peripheral)		Nervous system disorders - Other (neuropathy peripheral) (Gr 2)
	Paresthesia		
	Peripheral sensory neuropathy		Peripheral sensory neuropathy (Gr 2)
RESPIRATORY, THORACIC AND MEDIASTINAL DISORDERS			
	Dyspnea		
SKIN AND SUBCUTANEOUS TISSUE DISORDERS			
	Rash maculo-papular		

¹This table will be updated as the toxicity profile of the agent is revised. Updates will be distributed to all Principal Investigators at the time of revision. The current version can be obtained by contacting [contact]. Your name, the name of the investigator, the protocol and the agent should be included in the e-mail.

²Corneal disorder includes corneal cyst, corneal deposits, corneal epithelial microcysts, corneal epitheliopathy, corneal epithelium defect, corneal erosion, corneal intraepithelial microcysts, corneal neovascularization, corneal opacity, and corneal verticillata.

Adverse events reported on anetumab raptansine (BAY 94-9343) trials, but for which there is insufficient evidence to suggest that there was a reasonable possibility that anetumab raptansine (BAY 94-9343) caused the adverse event:

BLOOD AND LYMPHATIC SYSTEM DISORDERS - Disseminated intravascular coagulation; Febrile neutropenia

CARDIAC DISORDERS - Atrial fibrillation; Chest pain - cardiac; Palpitations; Pericardial effusion; Pericarditis; Sinus tachycardia; Supraventricular tachycardia

EAR AND LABYRINTH DISORDERS - Tinnitus; Vertigo

ENDOCRINE DISORDERS - Hypothyroidism

EYE DISORDERS - Cataract; Eye disorders - Other (blepharitis); Eye disorders - Other (eye irritation); Eye disorders - Other (eye pruritus); Eye disorders - Other (keratopathy); Eye disorders - Other (macular degeneration); Eye disorders - Other (ocular hyperemia); Eye disorders - Other (Schirmer's test abnormal); Eye pain; Floaters; Photophobia; Retinal vascular disorder; Vision decreased

GASTROINTESTINAL DISORDERS - Abdominal distension; Ascites; Dry mouth; Dyspepsia; Esophagitis; Flatulence; Gastritis; Mucositis oral; Periodontal disease

GENERAL DISORDERS AND ADMINISTRATION SITE CONDITIONS - Chills; Edema limbs; Flu like symptoms; Gait disturbance; General disorders and administration site conditions - Other (general physical health deterioration); Infusion site extravasation; Malaise; Non-cardiac chest pain; Pain

HEPATOBILIARY DISORDERS - Hepatic failure; Hepatobiliary disorders - Other (hepatocellular injury)

IMMUNE SYSTEM DISORDERS - Allergic reaction; Anaphylaxis

INFECTIONS AND INFESTATIONS - Bronchial infection; Conjunctivitis; Sepsis; Skin infection; Thrush; Urinary tract infection

INJURY, POISONING AND PROCEDURAL COMPLICATIONS - Bruising; Fall

INVESTIGATIONS - Cholesterol high; Creatinine increased; Ejection fraction decreased; Electrocardiogram QT corrected interval prolonged; Electrocardiogram T wave abnormal; GGT increased; Serum amylase increased

METABOLISM AND NUTRITION DISORDERS - Dehydration; Hypercalcemia; Hyperglycemia; Hypertriglyceridemia; Hyperuricemia; Hypoalbuminemia; Hypokalemia; Hypomagnesemia; Hyponatremia; Hypophosphatemia; Tumor lysis syndrome

MUSCULOSKELETAL AND CONNECTIVE TISSUE DISORDERS - Back pain; Flank pain; Generalized muscle weakness; Joint range of motion decreased; Pain in extremity

NEOPLASMS BENIGN, MALIGNANT AND UNSPECIFIED (INCL CYSTS AND POLYPS) - Tumor pain

NERVOUS SYSTEM DISORDERS - Dizziness; Dysesthesia; Headache; Lethargy; Movements involuntary; Nervous system disorders - Other (neurotoxicity); Nervous system disorders - Other (polyneuropathy); Neuralgia; Peripheral motor neuropathy; Tremor

PSYCHIATRIC DISORDERS - Anxiety; Insomnia

RENAL AND URINARY DISORDERS - Proteinuria

RESPIRATORY, THORACIC AND MEDIASTINAL DISORDERS - Cough; Epistaxis; Hiccups; Hypoxia; Nasal congestion; Oropharyngeal pain; Pleural effusion; Pleuritic pain; Sinus disorder; Voice alteration

SKIN AND SUBCUTANEOUS TISSUE DISORDERS - Alopecia; Dry skin; Hyperhidrosis; Nail changes; Pruritus; Rash acneiform; Urticaria

VASCULAR DISORDERS - Flushing; Hypertension; Hypotension; Thromboembolic event

Note: Anetumab raptansine (BAY 94-9343) in combination with other agents could cause an exacerbation of any adverse event currently known to be caused by the other agent, or the combination may result in events never previously associated with either agent.

7.1.2 Comprehensive Adverse Events and Potential Risks list (CAEPR) for MK-3475 (pembrolizumab, NSC 776864)

The Comprehensive Adverse Events and Potential Risks list (CAEPR) provides a single list of reported and/or potential adverse events (AE) associated with an agent using a uniform presentation of events by body system. In addition to the comprehensive list, a subset, the Specific Protocol Exceptions to Expedited Reporting (SPEER), appears in a separate column and is identified with bold and italicized text. This subset of AEs (SPEER) is a list of events that are protocol specific exceptions to expedited reporting to NCI (except as noted below). Refer to the 'CTEP, NCI Guidelines: Adverse Event Reporting Requirements' http://ctep.cancer.gov/protocolDevelopment/electronic_applications/docs/aeguidelines.pdf for further clarification. Frequency is provided based on 3793 patients. Below is the CAEPR for MK-3475 (pembrolizumab).

NOTE: Report AEs on the SPEER **ONLY IF** they exceed the grade noted in parentheses next to the AE in the SPEER. If this CAEPR is part of a combination protocol using multiple investigational agents and has an AE listed on different SPEERs, use the lower of the grades to determine if expedited reporting is required.

Version 2.6, July 15, 2021¹

Adverse Events with Possible Relationship to MK-3475 (pembrolizumab) (CTCAE 5.0 Term) [n= 3793]			Specific Protocol Exceptions to Expedited Reporting (SPEER)
Likely (>20%)	Less Likely (<=20%)	Rare but Serious (<3%)	
BLOOD AND LYMPHATIC SYSTEM DISORDERS			
	Anemia ²		
		Blood and lymphatic system disorders - Other (immune thrombocytopenic purpura) ²	
	Lymph node pain ²		
CARDIAC DISORDERS			
		Myocarditis ²	
		Pericarditis ²	

Adverse Events with Possible Relationship to MK-3475 (pembrolizumab) (CTCAE 5.0 Term) [n= 3793]			Specific Protocol Exceptions to Expedited Reporting (SPEER)
Likely (>20%)	Less Likely (<=20%)	Rare but Serious (<3%)	
ENDOCRINE DISORDERS			
	Adrenal insufficiency ²		
	Endocrine disorders - Other (thyroiditis) ²		
	Hyperthyroidism ²		
	Hypophysitis ²		
	Hypopituitarism ²		
	Hypothyroidism ²		
EYE DISORDERS			
		Uveitis ²	
		Eye disorders - Other (Vogt-Koyanagi-Harada syndrome)	
GASTROINTESTINAL DISORDERS			
	Abdominal pain		
	Colitis ²		
	Diarrhea ²		Diarrhea² (Gr 2)
	Mucositis oral ²		
	Nausea		Nausea (Gr 2)
	Pancreatitis ²		
	Small intestinal mucositis ²		
GENERAL DISORDERS AND ADMINISTRATION SITE CONDITIONS			
	Chills ²		
Fatigue			Fatigue (Gr 2)
	Fever ²		
HEPATOBILIARY DISORDERS			
	Hepatobiliary disorders - Other (autoimmune hepatitis) ²		
		Hepatobiliary disorders - Other (sclerosing cholangitis)	
IMMUNE SYSTEM DISORDERS			
		Anaphylaxis ²	
		Cytokine release syndrome ²	
		Immune system disorders - Other (acute graft-versus-host-disease) ^{2,3}	
		Immune system disorders - Other (hemophagocytic lymphohistiocytosis) ²	
	Immune system disorders - Other (pseudoprogression/tumor inflammation) ²		
	Immune system disorders - Other (sarcoidosis) ²		
		Serum sickness ²	
INFECTIONS AND INFESTATIONS			
	Infection ⁴		
INJURY, POISONING AND PROCEDURAL COMPLICATIONS			
		Infusion related reaction	
INVESTIGATIONS			
	Alanine aminotransferase increased ²		
	Alkaline phosphatase increased		

Adverse Events with Possible Relationship to MK-3475 (pembrolizumab) (CTCAE 5.0 Term) [n= 3793]			Specific Protocol Exceptions to Expedited Reporting (SPEER)
Likely (>20%)	Less Likely (<=20%)	Rare but Serious (<3%)	
	Aspartate aminotransferase increased ²		
	Blood bilirubin increased		
	CPK increased		
		GGT increased	
		Serum amylase increased	
METABOLISM AND NUTRITION DISORDERS			
	Anorexia		
	Hyponatremia		
		Metabolism and nutrition disorders - Other (diabetic ketoacidosis) ²	
		Metabolism and nutrition disorders - Other (type 1 diabetes mellitus) ²	
MUSCULOSKELETAL AND CONNECTIVE TISSUE DISORDERS			
	Arthralgia ²		Arthralgia² (Gr 2)
	Arthritis ²		
	Avascular necrosis ²		
	Back pain		
	Joint effusion ²		
	Joint range of motion decreased		
	Musculoskeletal and connective tissue disorder - Other (tenosynovitis) ²		
	Myalgia ²		
	Myositis ²		
NERVOUS SYSTEM DISORDERS			
		Guillain-Barre syndrome ²	
		Nervous system disorders - Other (myasthenic syndrome) ²	
		Nervous system disorders - Other (neuromyopathy) ²	
		Nervous system disorders - Other (non-infectious encephalitis) ²	
		Nervous system disorders - Other (non-infectious meningitis) ²	
		Nervous system disorders - Other (non-infectious myelitis)	
		Nervous system disorders - Other (polyneuropathy) ²	
		Paresthesia	
		Peripheral motor neuropathy ²	
RENAL AND URINARY DISORDERS			
		Renal and urinary disorders - Other (autoimmune nephritis) ²	
RESPIRATORY, THORACIC AND MEDIASTINAL DISORDERS			
	Cough		
	Pleuritic pain ²		
	Pneumonitis ²		
SKIN AND SUBCUTANEOUS TISSUE DISORDERS			
	Bullous dermatitis ²		

Adverse Events with Possible Relationship to MK-3475 (pembrolizumab) (CTCAE 5.0 Term) [n= 3793]			Specific Protocol Exceptions to Expedited Reporting (SPEER)
Likely (>20%)	Less Likely (<=20%)	Rare but Serious (<3%)	
		Erythema multiforme ²	
	Erythroderma	Palmar-plantar erythrodysesthesia syndrome	
	Pruritus ²		Pruritus² (Gr 2)
	Rash acneiform ²		
	Rash maculo-papular ²		Rash maculo-papular² (Gr 2)
	Skin and subcutaneous tissue disorders - Other (dermatitis) ²		
	Skin hypopigmentation ²		
		Stevens-Johnson syndrome ²	
		Toxic epidermal necrolysis	
	Urticaria ²		
VASCULAR DISORDERS		Vasculitis ²	

¹This table will be updated as the toxicity profile of the agent is revised. Updates will be distributed to all Principal Investigators at the time of revision. The current version can be obtained by contacting [contact]. Your name, the name of the investigator, the protocol and the agent should be included in the e-mail.

²Immune-mediated adverse reactions have been reported in patients receiving MK-3475 (pembrolizumab). Adverse events potentially related to MK-3475 (pembrolizumab) may be manifestations of immune-mediated adverse events. In clinical trials, most immune-mediated adverse reactions were reversible and managed with interruptions of MK-3475 (pembrolizumab), administration of corticosteroids and supportive care.

³Acute graft-versus-host disease has been observed in patients treated with MK-3475 (pembrolizumab) who received hematopoietic stem cell transplants.

⁴Infection includes all 75 sites of infection under the INFECTIONS AND INFESTATIONS SOC.

Adverse events reported on MK-3475 (pembrolizumab) trials, but for which there is insufficient evidence to suggest that there was a reasonable possibility that MK-3475 (pembrolizumab) caused the adverse event:

BLOOD AND LYMPHATIC SYSTEM DISORDERS - Blood and lymphatic system disorders - Other (pancytopenia); Disseminated intravascular coagulation; Hemolysis

CARDIAC DISORDERS - Atrial fibrillation; Cardiac arrest; Chest pain - cardiac; Heart failure; Myocardial infarction; Pericardial effusion; Pericardial tamponade; Ventricular arrhythmia

EYE DISORDERS - Eye pain

GASTROINTESTINAL DISORDERS - Abdominal distension; Ascites; Constipation; Duodenal hemorrhage; Dysphagia; Gastritis; Gastrointestinal disorders - Other (diverticulitis); Gastrointestinal disorders - Other (intestinal obstruction); Gastrointestinal disorders - Other (intussusception); Oral pain; Rectal hemorrhage; Small intestinal perforation; Upper gastrointestinal hemorrhage; Vomiting

GENERAL DISORDERS AND ADMINISTRATION SITE CONDITIONS - Edema face; Edema limbs; Facial pain; Gait disturbance; General disorders and administration site conditions - Other (general physical health deterioration); Generalized edema; Malaise; Non-cardiac chest pain; Pain

INVESTIGATIONS - Cholesterol high; Creatinine increased; Fibrinogen decreased; Lymphocyte count decreased; Neutrophil count decreased; Platelet count decreased; Weight loss; White blood cell decreased

METABOLISM AND NUTRITION DISORDERS - Dehydration; Hypercalcemia; Hyperglycemia;

Hyperkalemia; Hypertriglyceridemia; Hyperuricemia; Hypoalbuminemia; Hypokalemia; Hypophosphatemia; Metabolism and nutrition disorders - Other (failure to thrive); Tumor lysis syndrome

MUSCULOSKELETAL AND CONNECTIVE TISSUE DISORDERS - Bone pain; Generalized muscle weakness; Musculoskeletal and connective tissue disorder - Other (groin pain); Pain in extremity

NERVOUS SYSTEM DISORDERS - Aphonia; Depressed level of consciousness; Dysarthria; Edema cerebral; Encephalopathy; Headache; Hydrocephalus; Lethargy; Meningismus; Nervous system disorders - Other (brainstem herniation); Seizure; Syncope; Tremor

PSYCHIATRIC DISORDERS - Agitation; Confusion

RENAL AND URINARY DISORDERS - Acute kidney injury; Nephrotic syndrome; Proteinuria; Renal and urinary disorders - Other (hydronephrosis); Urinary incontinence; Urinary tract pain

REPRODUCTIVE SYSTEM AND BREAST DISORDERS - Pelvic pain

RESPIRATORY, THORACIC AND MEDIASTINAL DISORDERS - Dyspnea; Hypoxia; Laryngeal inflammation; Pleural effusion; Pneumothorax; Respiratory failure

SKIN AND SUBCUTANEOUS TISSUE DISORDERS - Alopecia; Dry skin; Skin and subcutaneous tissue disorders - Other (drug eruption)

VASCULAR DISORDERS - Hypertension; Peripheral ischemia; Thromboembolic event

Note: MK-3475 (pembrolizumab) in combination with other agents could cause an exacerbation of any adverse event currently known to be caused by the other agent, or the combination may result in events never previously associated with either agent.

